The variance is computed as a function of the within imputation variance and the between imputation variance. The estimate of the within imputation variance is given by the following.

$$\bar{U} = \frac{1}{m} \sum_{i=1}^m \hat{U}_i$$

where U_i is the variance of the difference in the i th imputation and is given by the following.

$$U_i = \frac{p_{it}(1-p_{it})}{229} + \frac{p_{ic}(1-p_{ic})}{231}$$

and p_{it} and p_{ic} are the proportions of patient with serious or significant adverse events in the Optimizer and Control groups respectively.

The between imputation variance is obtained by the following formula.

$$B = \frac{1}{m-1} \sum_{i=1}^m (\hat{Q}_i - \bar{Q})^2$$

The total variance is given by the following formula.

$$T = \bar{U} + \left(1 + \frac{1}{m}\right)B$$

and the z-statistic is given by the following.

$$z = \frac{(\bar{Q})}{\sqrt{T}}$$

When these imputations are combined the $z = -0.4839$ with a corresponding P-value of 0.3142.

The mean values for the ITT ten imputations for patients with baseline $EF \geq 25$ are presented below.

Table XII.2a Mean AT at Study Time Points with EF \geq 25 at Baseline

Imputation	Time	Control Mean (SD) N Med (Min, Max)	Optimizer Mean (SD) N Med (Min, Max)	P-value
ITT1	Baseline	11.14 (2.31) 113 10.73 (5.40, 17.05)	10.76 (2.12) 117 10.44 (5.29, 16.08)	0.1909 ¹
	24 Week	10.69 (2.09) 113 10.64 (4.79, 15.50)	10.95 (2.38) 117 10.50 (5.01, 19.82)	0.3763 ¹
	24 Week Difference From Baseline	-0.45 (2.02) 113 -0.33 (-7.29, 5.64)	0.19 (2.45) 117 -0.08 (-4.65, 9.17)	0.0152 ²
ITT2	Baseline	11.17 (2.29) 113 10.76 (5.40, 17.05)	10.74 (2.18) 117 10.44 (5.29, 16.09)	0.1492 ¹
	24 Week	10.73 (2.09) 113 10.64 (6.24, 15.50)	10.83 (2.44) 117 10.39 (5.01, 19.82)	0.7332 ¹
	24 Week Difference From Baseline	-0.44 (2.12) 113 -0.33 (-5.68, 5.64)	0.09 (2.35) 117 -0.14 (-4.65, 8.94)	0.0374 ³
ITT3	Baseline	11.14 (2.31) 113 10.73 (5.40, 17.05)	10.73 (2.09) 117 10.52 (5.29, 16.08)	0.1620 ¹
	24 Week	10.75 (2.12) 113 10.47 (5.99, 15.50)	10.83 (2.37) 117 10.41 (4.97, 19.82)	0.7812 ¹
	24 Week Difference From Baseline	-0.39 (2.12) 113 -0.31 (-6.10, 5.64)	0.10 (2.44) 117 -0.08 (-4.65, 8.94)	0.0533 ³
ITT4	Baseline	11.14 (2.31) 113 10.73 (5.40, 17.05)	10.75 (2.12) 117 10.52 (5.29, 16.08)	0.1864 ¹
	24 Week	10.66 (2.15) 113 10.33 (6.24, 15.79)	10.83 (2.45) 117 10.39 (4.10, 19.82)	0.5746 ¹
	24 Week Difference From Baseline	-0.48 (2.23) 113 -0.31 (-6.03, 6.60)	0.08 (2.33) 117 -0.11 (-4.65, 8.94)	0.0328 ³

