ITT3	12/113 (10.62)	24/117 (20.51)	0.0292
ITT4	10/113 (8.85)	24/117 (20.51)	0.0100
ITT5	11/113 (9.73)	26/117 (22.22)	0.0078
ITT6	10/113 (8.85)	23/117 (19.66)	0.0151
ITT7	13/113 (11.50)	23/117 (19.66)	0.0637
ITT8	10/113 (8.85)	25/117 (21.37)	0.0065
ITT9	11/113 (9.73)	27/117 (23.08)	0.0050
ITT10	14/113 (12.39)	24/117 (20.51)	0.0689

¹One-sided Fisher's exact test

The combination of the 10 ITT imputations in sub-groups by EF, the resulting z = -1.9432 with a corresponding P-value of 0.0260.

The means for the ITT ten imputations with baseline EF \geq 25 and NYHA=3 are presented below.

Table XII.3a Mean AT at Study Time Points with EF \geq 25 and NYHA=3 at Baseline

Imputation	Time	Control Mean (SD) N Med (Min, Max)	Optimizer Mean (SD) N Med (Min, Max)	P-value
ITT1	Baseline	11.19 (2.19) 97 10.73 (7.22, 16.72)	10.72 (2.11) 109 10.44 (5.29, 16.05)	0.1199 ¹
	24 Week	10.70 (2.14) 97 10.47 (4.79, 15.50)	10.98 (2.43) 109 10.57 (5.01, 19.82)	0.3783 ¹
	24 Week Difference From Baseline	-0.49 (1.97) 97 -0.38 (-7.29, 4.62)	0.27 (2.51) 109 -0.02 (-4.65, 9.17)	0.0086²
ITT2	Baseline	11.22 (2.17) 97 10.76 (7.22, 16.72)	10.71 (2.17) 109 10.44 (5.29, 16.09)	0.0916 ¹
	24 Week	10.77 (2.11) 97 10.53 (6.24, 15.50)	10.89 (2.48) 109 10.42 (5.01, 19.82)	0.7109 ¹
	24 Week Difference From Baseline	-0.45 (2.06) 97 -0.38 (-5.68, 4.62)	0.18 (2.38) 109 -0.08 (-4.65, 8.94)	0.0218³
ITT3	Baseline	11.19 (2.19) 97 10.73 (7.22, 16.72)	10.68 (2.07) 109 10.44 (5.29, 16.05)	0.0884 ¹
	24 Week	10.76 (2.18) 97 10.33 (5.99, 15.50)	10.84 (2.41) 109 10.42 (4.97, 19.82)	0.8043 ¹
	24 Week Difference From Baseline	-0.42 (2.11) 97 -0.31 (-6.10, 4.62)	0.16 (2.45) 109 -0.02 (-4.65, 8.94)	0.0336 ³
ITT4	Baseline	11.19 (2.19) 97 10.73 (7.22, 16.72)	10.70 (2.11) 109 10.44 (5.29, 16.05)	0.1067 ¹
	24 Week	10.76 (2.16) 97 10.35 (6.24, 15.79)	10.85 (2.51) 109 10.42 (4.10, 19.82)	0.7673 ¹
	24 Week Difference From Baseline	-0.43 (2.16) 97 -0.27 (-6.03, 6.60)	0.15 (2.38) 109 -0.07 (-4.65, 8.94)	0.0344 ³
ITT5	Baseline	11.22 (2.17) 97 10.76 (7.22, 16.72)	10.69 (2.13) 109 10.39 (5.29, 16.05)	0.0779 ¹
	24 Week	10.77 (2.10) 97 10.35 (6.24, 15.50)	10.93 (2.37) 109 10.62 (5.01, 19.82)	0.5946 ¹
	24 Week Difference From Baseline	-0.45 (1.92) 97 -0.31 (-5.17, 4.62)	0.24 (2.34) 109 -0.02 (-4.65, 8.94)	0.0099²
ITT6	Baseline	11.19 (2.19) 97 10.73 (7.22, 16.72)	10.70 (2.09) 109 10.44 (5.29, 16.05)	0.1075 ¹
	24 Week	10.65 (2.10) 97 10.35 (6.24, 15.50)	10.83 (2.58) 109 10.41 (4.10, 19.82)	0.5872 ⁴

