Combining the sub-groups from the ten imputations for EF \geq 25 with NYHA=3 we get a z = -2.2624 with at corresponding P-value of 0.0118.

For the FASA population, the ten imputations for the whole population, EF \geq 25, and EF \geq 25 with NYHA=3 are presented in the tables below. The means are presented in the table below.

Table XII.4a Mean AT at Study Time Points

Imputation	Time	Control Mean (SD) N Med (Min, Max)	Optimizer Mean (SD) N Med (Min, Max)	P-value
FASA1	Baseline	10.90 (2.29) 212 10.60 (4.10, 17.05)	10.90 (2.33) 208 10.62 (4.10, 16.92)	0.9798 ¹
	24 Week ³	10.75 (2.27) 212 10.79 (4.10, 19.61)	10.81 (2.46) 207 10.40 (4.10, 19.82)	0.7763 ¹
	24 Week Difference From Baseline	-0.15 (2.26) 212 -0.20 (-7.29, 9.34)	-0.08 (2.38) 208 -0.12 (-6.91, 9.17)	0.3784 ²
FASA2	Baseline	10.90 (2.27) 212 10.69 (4.10, 17.05)	10.89 (2.36) 208 10.60 (4.10, 16.92)	0.9516 ¹
	24 Week ³	10.74 (2.25) 212 10.73 (4.10, 19.61)	10.80 (2.51) 207 10.41 (4.10, 19.82)	0.8209 ¹
	24 Week Difference From Baseline	-0.16 (2.25) 212 -0.20 (-5.68, 9.34)	-0.10 (2.32) 208 -0.14 (-6.55, 8.94)	0.3936 ²
FASA3	Baseline	10.92 (2.29) 212 10.72 (4.10, 17.05)	10.90 (2.32) 208 10.72 (4.10, 16.92)	0.9138 ¹
	24 Week ³	10.80 (2.29) 212 10.62 (4.10, 19.61)	10.81 (2.48) 207 10.42 (4.10, 19.82)	0.9686 ¹
	24 Week Difference From Baseline	-0.12 (2.28) 212 -0.20 (-6.10, 9.34)	-0.09 (2.32) 208 -0.10 (-6.47, 8.94)	0.4404 ²
FASA4	Baseline	10.91 (2.27) 212 10.73 (4.10, 17.05)	10.90 (2.31) 208 10.60 (4.10, 16.92)	0.9661 ¹
	24 Week ³	10.72 (2.30) 212 10.57 (4.10, 19.61)	10.81 (2.50) 207 10.42 (4.10, 19.82)	0.7222 ¹
	24 Week Difference From Baseline	-0.19 (2.28) 212 -0.13 (-6.03, 9.34)	-0.10 (2.34) 208 -0.12 (-6.47, 8.94)	0.3447 ²
FASA5	Baseline	10.94 (2.28) 212 10.73 (4.10, 17.05)	10.92 (2.31) 208 10.61 (4.10, 16.92)	0.9293 ¹
	24 Week ³	10.70 (2.31) 212 10.57 (4.10, 19.61)	10.82 (2.44) 207 10.49 (4.10, 19.82)	0.6161 ¹
	24 Week Difference From Baseline	-0.24 (2.20) 212 -0.15 (-8.59, 9.34)	-0.11 (2.29) 208 -0.14 (-6.88, 8.94)	0.2778 ²
FASA6	Baseline	10.90 (2.27) 212 10.69 (4.10, 17.05)	10.89 (2.31) 208 10.59 (4.10, 16.92)	0.9437 ¹
	24 Week ³	10.70 (2.28) 212 10.67 (4.10, 19.61)	10.74 (2.55) 207 10.39 (4.10, 19.82)	0.8434 ¹
	24 Week Difference From Baseline	-0.21 (2.23) 212 -0.20 (-5.13, 9.34)	-0.15 (2.44) 208 -0.14 (-8.23, 8.94)	0.4052 ²
FASA7	Baseline	10.89 (2.31) 212 10.69(4.10, 17.05)	10.91 (2.34) 208 10.66 (4.10, 16.92)	0.9239 ¹

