	24 Week ³	10.82 (2.29) 212 10.81 (4.10, 19.61)	10.78 (2.48) 207 10.40 (4.10, 19.82)	0.8756 ¹
	24 Week Difference From Baseline	-0.07 (2.32) 212 -0.11 (-6.65, 9.34)	-0.13 (2.36) 208 -0.10 (-7.99, 8.94)	0.6140 ²
FASA8	Baseline	10.95 (2.28) 212 10.74 (4.10, 17.05)	10.86 (2.34) 208 10.60 (4.10, 16.92)	0.6683 ¹
	24 Week ³	10.68 (2.28) 212 10.56 (4.10, 19.61)	10.71 (2.51) 207 10.38 (4.10, 19.82)	0.9027 ¹
	24 Week Difference From Baseline	-0.27 (2.23) 212 -0.23 (-6.71, 9.34)	-0.15 (2.43) 208 -0.17 (-6.91, 8.94)	0.2947 ²

Table XII.4a Mean AT at Study Time Points (Continued)

Imputation	Time	Control Mean (SD) N Med (Min, Max)	Optimizer Mean (SD) N Med (Min, Max)	P-value
FASA9	Baseline	10.94 (2.28) 212 10.73 (4.10, 17.05)	10.91 (2.32) 208 10.60 (4.10, 16.92)	0.8806 ¹
	24 Week ³	10.72 (2.22) 212 10.73 (4.10, 19.61)	10.83 (2.52) 207 10.41 (4.10, 19.82)	0.6582 ¹
	24 Week Difference From Baseline	-0.22 (2.15) 212 -0.23 (-5.04, 9.34)	-0.08 (2.29) 208 -0.15 (-6.51, 8.94)	0.2612 ²
FASA10	Baseline	10.90 (2.28) 212 10.60 (4.10, 17.05)	10.91 (2.30) 208 10.59 (4.10, 16.92)	0.9748 ¹
	24 Week ³	10.69 (2.33) 212 10.67 (4.10, 19.61)	10.79 (2.46) 207 10.42 (4.10, 19.82)	0.6820 ¹
	24 Week Difference From Baseline	-0.21 (2.34) 212 -0.15 (-8.59, 9.34)	-0.11 (2.23) 208 -0.24 (-6.47, 8.94)	0.3337 ²

¹Two-sided equal variance Student's t-test.²One-sided equal variance Student's t-test³One patient in the Optimizer group had a difference imputed but did not have a 24 week AT imputed.

The responder analysis for the 10 imputations appears below.

Table XII.4b Univariate Primary Effectiveness Endpoint Results (≥20% Improvement) for FASA Patients

Population	Control n/N (%)	Optimizer n/N (%)	P-value ¹
FASA1	28/212 (13.21)	37/208 (17.79)	0.1224
FASA2	31/212 (14.62)	35/208 (16.83)	0.3133
FASA3	29/212 (13.68)	37/208 (17.79)	0.1532
FASA4	26/212 (12.26)	37/208 (17.79)	0.0736
FASA5	27/212 (12.74)	39/208 (18.75)	0.0593
FASA6	26/212 (12.26)	35/208 (16.83)	0.1173
FASA7	30/212 (14.15)	36/208 (17.31)	0.2253
FASA8	24/212 (11.32)	38/208 (18.27)	0.0305
FASA9	27/212 (12.74)	39/208 (18.75)	0.0593
FASA10	33/212 (15.57)	36/208 (17.31)	0.3632

¹One-sided Fisher's exact test

The combined imputations for the FASA patients resulted in a z = -0.4745 with a corresponding P=0.3176.

The means for the FASA ten imputations with baseline EF≥25 are presented below.

Table XII.5a Mean AT at Study Time Points with EF \geq 25 at Baseline

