	24 Week Difference From Baseline	-0.58 (2.22) 112 -0.33 (-6.71, 5.85)	0.11 (2.53) 112 -0.15 (-5.36, 8.94)	0.0148 ³

Table XII.5a Mean AT at Study Time Points with EF \geq 25 at Baseline

Imputation	Time	Control Mean (SD) N Med (Min, Max)	Optimizer Mean (SD) N Med (Min, Max)	P-value
FASA9	Baseline	11.21 (2.31) 112 10.79 (5.40, 17.05)	10.74 (2.17) 112 10.42 (5.29, 16.08)	0.1130 ¹
	24 Week	10.70 (2.02) 112 10.58 (6.24, 15.50)	10.92 (2.47) 112 10.42 (5.01, 19.82)	0.4599 ⁴
	24 Week Difference From Baseline	-0.52 (2.09) 112 -0.43 (-5.04, 5.64)	0.18 (2.41) 112 -0.09 (-4.65, 8.94)	0.0106 ²
FASA10	Baseline	11.16 (2.31) 112 10.74 (5.40, 17.05)	10.74 (2.17) 112 10.42 (5.29, 16.08)	0.1687 ¹
	24 Week	10.64 (2.14) 112 10.39 (5.92, 15.50)	10.78 (2.40) 112 10.39 (5.01, 19.82)	0.6452 ¹
	24 Week Difference From Baseline	-0.52 (2.27) 112 -0.43 (-6.17, 5.64)	0.03 (2.31) 112 -0.16(-4.65, 8.94)	0.0358 ³

¹Two-sided equal variance Student's t-test.²One-sided unequal variance Student's t-test³One-sided equal variance Student's t-test⁴Two-sided unequal variance Student's t-test

The responder analysis for the 10 imputations appears below.

Table XII.5b Univariate Primary Effectiveness Endpoint Results (\geq 20% Improvement) for FASA Patients with EF \geq 25

Population	Control n/N (%)	Optimizer n/N (%)	P-value ¹
FASA1	9/112 (8.04)	23/112 (20.54)	0.0061
FASA2	14/112 (12.50)	22/112 (19.64)	0.1012
FASA3	12/112 (10.71)	23/112 (20.54)	0.0323
FASA4	10/112 (8.93)	23/112 (20.54)	0.0113
FASA5	11/112 (9.82)	25/112 (22.32)	0.0086
FASA6	10/112 (8.93)	22/112 (19.64)	0.0172
FASA7	13/112 (11.61)	23/112 (20.54)	0.0503
FASA8	10/112 (8.93)	24/112 (21.43)	0.0073
FASA9	11/112 (9.82)	26/112 (23.21)	0.0055
FASA10	14/112 (12.50)	23/112 (20.54)	0.0747

¹One-sided Fisher's exact test

Combining these ten imputations for EF \geq 25 a z = -1.9292 with a P-value of 0.0269.

The means for the FASA ten imputations with baseline EF \geq 25 and NYHA=3 are presented below.

Table XII.6a Mean AT at Study Time Points with EF \geq 25 and NYHA=3 at Baseline

Imputation	Time	Control Mean (SD) N Med (Min, Max)	Optimizer Mean (SD) N Med (Min, Max)	P-value
FASA1	Baseline	11.21 (2.19) 96 10.74 (7.22, 16.72)	10.68 (2.11) 104 10.42 (5.29, 16.05)	0.0877 ¹
	24 Week	10.72 (2.14) 96 10.50 (4.79, 15.50)	10.96 (2.46) 104 10.46 (5.01, 19.82)	0.4646 ¹
	24 Week Difference From Baseline	-0.49 (1.98) 96 -0.40 (-7.29, 4.62)	0.27 (2.56) 104 -0.01 (-4.65, 9.17)	0.0094 ²

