	24 Week Difference From Baseline	-0.53 (1.99) 96 -0.49 (-5.04, 5.11)	0.20 (2.46) 104 -0.09 (-4.65, 8.94)	0.0121 ²
FASA10	Baseline	11.21 (2.20) 96 10.74 (7.22, 16.72)	10.72 (2.14) 104 10.42 (5.29, 16.05)	0.1122 ¹
	24 Week	10.67 (2.15) 96 10.32 (6.24, 15.50)	10.83 (2.44) 104 10.42 (5.01, 19.82)	0.6355 ¹
	24 Week Difference From Baseline	-0.54 (2.22) 96 -0.49 (-6.17, 5.50)	0.11 (2.35) 104 -0.12 (-4.65, 8.94)	0.0240 ²

¹Two-sided equal variance Student's t-test.²One-sided unequal variance Student's t-test³One-sided equal variance Student's t-test⁴Two-sided unequal variance Student's t-test.

The responder analysis for the 10 imputations appears below.

Table XII.6b Univariate Primary Effectiveness Endpoint Results (\geq 20% Improvement) for FASA Patients with EF \geq 25 and NYHA=3 at Baseline

Population	Control n/N (%)	Optimizer n/N (%)	P-value ¹
FASA1	7/96 (7.29)	23/104 (22.12)	0.0027
FASA2	11/96 (11.46)	22/104 (21.15)	0.0481
FASA3	10/96 (10.42)	22/104 (21.15)	0.0294
FASA4	8/96 (8.33)	23/104 (22.12)	0.0057
FASA5	9/96 (9.38)	24/104 (23.08)	0.0072
FASA6	8/96 (8.33)	21/104 (20.19)	0.0137
FASA7	11/96 (11.46)	22/104 (21.15)	0.0481
FASA8	8/96 (8.33)	22/104 (21.15)	0.0089
FASA9	8/96 (8.33)	24/104 (23.08)	0.0036
FASA10	11/96 (11.46)	23/104 (22.12)	0.0338

¹One-sided Fisher's exact test

The combination of the 10 imputations for the sub-group of FASA EF \geq 25 and NYHA=3 yields a z = -2.2512 with a P = 0.0121.

For the FASB population, the ten imputations for the whole population, EF \geq 25, and EF \geq 25 with NYHA=3 are presented in the tables below. The means are presented in the table below.

Table XII.7a Mean AT at Study Time Points

Imputation	Time	Control Mean (SD) N Med (Min, Max)	Optimizer Mean (SD) N Med (Min, Max)	P-value
FASB1	Baseline	10.87 (2.30) 207 10.54 (4.10, 17.05)	10.90 (2.33) 208 10.62 (4.10, 16.92)	0.8975 ¹
	24 Week ³	10.74 (2.27) 207 10.78 (4.10, 19.61)	10.81 (2.46) 207 10.40 (4.10, 19.82)	0.7419 ¹
	24 Week Difference From Baseline	-0.13 (2.23) 207 -0.17 (-7.29, 9.34)	-0.08 (2.38) 208 -0.12 (-6.91, 9.17)	0.4208 ²
FASB2	Baseline	10.87 (2.28) 207 10.56 (4.10, 17.05)	10.89 (2.36) 208 10.60 (4.10, 16.92)	0.9257 ¹
	24 Week ³	10.76 (2.26) 207 10.78 (4.10, 19.61)	10.80 (2.51) 207 10.41 (4.10, 19.82)	0.8944 ¹
	24 Week Difference From Baseline	-0.11 (2.24) 207 -0.12 (-5.68, 9.34)	-0.10 (2.32) 208 -0.14 (-6.55, 8.94)	0.4920 ²
FASB3	Baseline	10.89 (2.30) 207 10.65 (4.10, 17.05)	10.90 (2.32) 208 10.72 (4.10, 16.92)	0.9642 ¹

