	24 Week Difference From Baseline	-0.11 (2.22) 207 -0.12 (-6.03, 9.34)	-0.11 (2.23) 208 -0.24 (-6.47, 8.94)	0.5079 ²

¹Two-sided equal variance Student's t-test.

²One-sided equal variance Student's t-test

³One patient in the Optimizer group had a difference imputed but did not have a 24 week AT imputed.

The responder analysis for the 10 imputations appears below.

Table XII.7b Univariate Primary Effectiveness Endpoint Results ($\geq 20\%$ Improvement) for FASB Patients

Population	Control n/N (%)	Optimizer n/N (%)	P-value¹
FASB1	27/207 (13.04)	37/208 (17.79)	0.1145
FASB2	31/207 (14.98)	35/208 (16.83)	0.3516
FASB3	28/207 (13.53)	37/208 (17.79)	0.1447
FASB4	26/207 (12.56)	37/208 (17.79)	0.0888
FASB5	27/207 (13.04)	39/208 (18.75)	0.0726
FASB6	26/207 (12.56)	35/208 (16.83)	0.1381
FASB7	30/207 (14.49)	36/208 (17.31)	0.2580
FASB8	24/207 (11.59)	38/208 (18.27)	0.0381
FASB9	27/207 (13.04)	39/208 (18.75)	0.0726
FASB10	30/207 (15.94)	36/208 (17.31)	0.4046

¹One-sided Fisher's exact test

The total FASB population results in a combined $z = -0.4959$ with corresponding P-value of 0.3100.

The means for the FASB ten imputations with baseline $EF \geq 25$ are presented below.

Table XII.8a Mean AT at Study Time Points with EF \geq 25 at Baseline

Imputation	Time	Control Mean (SD) N Med (Min, Max)	Optimizer Mean (SD) N Med (Min, Max)	P-value
FASB1	Baseline	11.12 (2.33) 108 10.73 (5.40, 17.05)	10.73 (2.13) 112 10.42 (5.29, 16.08)	0.1970 ¹
	24 Week	10.65 (2.08) 108 10.58 (4.79, 15.50)	10.92 (2.41) 112 10.42 (5.01, 19.82)	0.3698 ¹
	24 Week Difference From Baseline	-0.46 (1.99) 108 -0.36 (-7.29, 5.64)	0.20 (2.49) 112 -0.08 (-4.65, 9.17)	0.0152 ²
FASB2	Baseline	11.15 (2.31) 108 10.74 (5.40, 17.05)	10.74 (2.21) 112 10.42 (5.29, 16.09)	0.1884 ¹
	24 Week	10.77 (2.10) 108 10.80 (6.24, 15.50)	10.82 (2.48) 112 10.37 (5.01, 19.82)	0.8676 ¹
	24 Week Difference From Baseline	-0.38 (2.12) 108 -0.29 (-5.68, 5.64)	0.08 (2.40) 112 -0.15 (-4.65, 8.94)	0.0688 ³
FASB3	Baseline	11.12 (2.33) 108 10.73 (5.40, 17.05)	10.73 (2.12) 112 10.48 (5.29, 16.08)	0.2045 ¹
	24 Week	10.72 (2.11) 108 10.49 (5.99, 15.50)	10.84 (2.41) 112 10.42 (4.97, 19.82)	0.6958 ¹
	24 Week Difference From Baseline	-0.39 (2.05) 108 -0.32 (-6.10, 5.64)	0.11 (2.47) 112 -0.09 (-4.65, 8.94)	0.0512 ³
FASB4	Baseline	11.12 (2.33) 108 10.73 (5.40, 17.05)	10.74 (2.14) 112 10.48 (5.29, 16.08)	0.2139 ¹
	24 Week	10.68 (2.19) 108 10.34 (6.24, 15.79)	10.83 (2.43) 112 10.40 (4.10, 19.82)	0.6299 ¹

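### Seven of the nine pooled multiple-imputation results in Section XII, including the whole-population ITT test, cannot be obtained from the report's own responder tables

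*Combined protocol and SAP*

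**What the plan says.** Section XII defines Q_i as the Optimizer minus control responder proportion in imputation i, with m = 10. It averages the Q_i, adds the mean within-imputation variance to 1 + 1/m times the between-imputation variance B, and divides the mean difference by the square root of the total T. The within-imputation variance is printed with denominators 229 (Optimizer) and 231 (control), and its proportions are described thus: "are the proportions of patient with serious or significant adverse events in the Optimizer and Control groups respectively".

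Nine pooled results follow, for three analysis sets by three groups:

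- ITT, whole population: "When these imputations are combined the $z = -0.4839$ with a corresponding P-value of 0.3142".
- ITT, EF≥25: "the resulting z = -1.9432 with a corresponding P-value of 0.0260".
- ITT, EF≥25 and NYHA=3: "we get a z = -2.2624 with at corresponding P-value of 0.0118".
- FASA, whole population: "The combined imputations for the FASA patients resulted in a z = -0.4745 with a corresponding P=0.3176".
- FASA, EF≥25: "z = -1.9292 with a P-value of 0.0269".
- FASA, EF≥25 and NYHA=3: "yields a z = -2.2512 with a P = 0.0121".
- FASB, whole population: "The total FASB population results in a combined $z = -0.4959$ with corresponding P-value of 0.3100".
- FASB, EF≥25: z = -1.9045, P = 0.0284.
- FASB, EF≥25 and NYHA=3: z = -2.1549, P = 0.0156.

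The section closes by saying that the whole population is not significant at 0.025, that EF≥25 lies a little above 0.025, and that EF≥25 with NYHA=3 is significant. Protocol IX.A.1 sets a one-sided alpha of 0.025.

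**The concern.** The ten ITT imputations in Table XII.1b each favour Optimizer, and their individual z-values run from 0.61 to 2.02. A pooled z of 0.48 is below all ten. Pooling can lower z when the imputations disagree strongly, but these ten differences lie close together.

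The whole-population ITT figure is the report's pooled test of what it labels its primary effectiveness endpoint. If it cannot be derived from the table beside it, neither that figure nor the other pooled values can be relied on until they are re-run. For EF≥25 the printed values also sit close enough to 0.025 that a modest error changes which side they fall on.

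**Working it through.** **Inputs.** Responder counts from Tables XII.1b to XII.9b, with the arm sizes shown in each table.

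**Formulas, from Section XII.** Q̄ = mean of Q_i; U_i = p_t(1−p_t)/n_t + p_c(1−p_c)/n_c; Ū = mean of U_i; B = Σ(Q_i − Q̄)²/9; T = Ū + 1.1B; z = Q̄/√T; P one-sided from the normal distribution. I used actual arm sizes for n_t and n_c.

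**Step 1: results that reproduce.** For ITT, EF≥25 and NYHA=3 (Table XII.3b), the ten control counts sum to 91 of 970 and the Optimizer counts to 234 of 1,090.

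- Q̄ = 0.21468 − 0.09381 = 0.12086 (from unrounded proportions); Ū = 0.002420; B = 0.000395
- T = 0.002420 + 1.1 × 0.000395 = 0.002854
- z = 0.12086/√0.002854 = 2.2624, as printed apart from sign

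The FASA counterpart gives 2.2512, also as printed. Two four-decimal matches identify the procedure and rule out rounding as the cause of the other differences.

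**Step 2: whole-population ITT.** Control counts are 28, 31, 29, 26, 27, 26, 30, 24, 27, 33 of 213 (sum 281). Optimizer counts are 37, 37, 38, 39, 40, 36, 36, 39, 40, 38 of 215 (sum 380).

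- Q̄ = 380/2,150 − 281/2,130 = 0.17674 − 0.13192 = 0.0448
- Ū = 0.001214; B = 0.000270; T = 0.001214 + 1.1 × 0.000270 = 0.001511
- z = 0.04482/√0.001511 = 1.153; P = 0.124

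**Step 3: can the printed 0.4839 arise from this table?** Holding Q̄ and Ū at the table's values:

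- Required T = (0.0448/0.4839)² = 0.00858, which is 5.7 times 0.00151
- Required B = (0.00858 − 0.001214)/1.1 = 0.0067
- The ten differences lie between 0.0218 and 0.0687 (range 0.0469), so B cannot exceed (0.0469/2)² × 10/9 = 0.00061
- Even at that maximum, z = 0.0448/√(0.001214 + 1.1 × 0.00061) ≈ 1.03

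**Step 4: all nine results** (signs dropped).

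| Set and group | Recomputed z, P | Printed z, P |
|---|---|---|
| ITT, all | 1.153, 0.124 | 0.4839, 0.3142 |
| ITT, EF≥25 | 2.039, 0.0207 | 1.9432, 0.0260 |
| ITT, EF≥25 and NYHA=3 | 2.2624, 0.0118 | 2.2624, 0.0118 |
| FASA, all | 1.133, 0.129 | 0.4745, 0.3176 |
| FASA, EF≥25 | 2.026, 0.0214 | 1.9292, 0.0269 |
| FASA, EF≥25 and NYHA=3 | 2.2512, 0.0122 | 2.2512, 0.0121 |
| FASB, all (33/207 in row 10) | 1.066, 0.143 | 0.4959, 0.3100 |
| FASB, EF≥25 | 1.953, 0.0254 | 1.9045, 0.0284 |
| FASB, EF≥25 and NYHA=3 | 2.195, 0.0141 | 2.1549, 0.0156 |

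**Step 5: the printed denominators.** With 229 and 231 taken literally, whole-population ITT gives z = 1.186, P = 0.118, and none of the nine values reproduces (ITT EF≥25 and NYHA=3 becomes 3.083). The denominators are therefore an error in the text and not the source of the wrong values. They would matter if used: for ITT EF≥25, T would fall from 0.00270 to 0.00161.

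**Step 6: two smaller errors.**

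- Table XII.7b, row FASB10, prints 30/207 for control beside 15.94% and P = 0.4046. But 30/207 is 14.49%, with Fisher P = 0.2580; 33/207 is 15.94%, with P = 0.4046. Using 30/207 gives a pooled FASB z of 1.132 (P = 0.129), which does not match the printed value either.
- Every pooled z is printed negative, although Q is Optimizer minus control and every difference is positive. The P-values are unaffected.

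Other variants also fail to reproduce the seven values: dropping B, other multipliers on B, a pooled-proportion variance, a continuity correction, a t reference, averaging the ten z-values, and pooling mean AT changes instead of responders.

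**The case against.** The strongest reply is that nothing decisive changes. P = 0.31 and P = 0.12 both miss 0.025, and the report already says the whole population is not significant. The only threshold crossings are in subgroups that should carry no confirmatory weight. That is right about the conclusion, but a pooled primary result that its own table rules out still has to be corrected.

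Three qualifications stand:

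- **Seven of nine is the lenient count, and it mixes sizes.** It depends on replacing 229 and 231 by the actual arm sizes; read literally, the formula reproduces none. The three whole-population gaps are large, ITT and FASA EF≥25 are moderate, and the two FASB subgroup gaps are small. Changing one count (FASB5 control from 9 to 11) brings FASB EF≥25 and NYHA=3 to 2.1548, close to the printed 2.1549.
- **The variance bound says nothing about cause.** It holds Q̄ and Ū at the table's values. One wrong input row would move Q̄ and B together. The bound shows only that Table XII.1b did not produce the printed figure; the values may come from another imputation run.
- **The endpoint is the report's own.** The pooled tables use a 20% or greater rise in AT, whereas Protocol IX.A.1 defines response as a rise of at least 1 ml O₂/kg/min in VT. The recomputed 0.124 is the report's pooled result corrected, and not a test of the protocol's definition.

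Table IX.1 refers to a Statistical Analysis Plan that is not otherwise shown, so whether the EF groups or FASA and FASB were specified there cannot be judged. The EF groups are not among the comparisons listed in Protocol IX.A.4, and the two FAS sets are defined only in the report.

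**Conclusion.** The concern holds. Seven of the nine pooled results in Section XII do not follow from the tables beside them, and the whole-population ITT value cannot do so: z should be 1.153 with P = 0.124, against the printed 0.4839 and 0.3142.

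The main conclusions survive. The whole population is non-significant in all three sets (P about 0.12 to 0.14), and EF≥25 with NYHA=3 stays below 0.025 in all three. The description of EF≥25 does not survive as written: it holds for FASB (0.0254), but the ITT and FASA tables give 0.0207 and 0.0214.

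This rests on the printed counts being the analysed counts, on actual arm sizes in the variance, and on 33/207 for FASB10. The documents do not show what produced the wrong values.

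**What to change.** 1. In the variance formula, replace 229 and 231 by the Optimizer and control sizes of each analysis set or subgroup, define the proportions as AT responders, and make the sign agree with the definition of Q.
2. Correct the FASB10 control count in Table XII.7b after checking it against the source.
3. Re-run all nine combinations from the stored imputations, printing Q̄, Ū, B and T beside each z. If the stored imputations differ from the tables, replace the tables as well.
4. Restate the closing paragraph of Section XII from the re-run. If the tables are right, it should say: whole population non-significant (P about 0.12 in ITT); EF≥25 narrowly below 0.025 in ITT and FASA and just above it in FASB; EF≥25 with NYHA=3 below 0.025 in all three.
5. State in the same paragraph that the EF groups are not among the protocol's listed comparisons and carry no confirmatory weight after a non-significant whole-population test, so a corrected subgroup P below 0.025 is not a positive trial result.

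The cost is a short calculation from existing data and a text correction.
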